### **Numeric Results for Wilcoxon Test (Normal Distribution)**

Null Hypothesis:  $\text{Mean0}=\text{Mean1}$     Alternative Hypothesis:  $\text{Mean0}\neq\text{Mean1}$

Unknown standard deviation.

| Power   | N  | Alpha | Beta    | Mean0 | Mean1 | SD | Effect Size |
|---------|----|-------|---------|-------|-------|----|-------------|
| 0.84466 | 24 | 0.05  | 0.15534 | 0     | 1.33  | 2  | 0.665       |
| 0.94694 | 24 | 0.05  | 0.05306 | 0     | 1.6   | 2  | 0.8         |

Safety and adverse event data will be summarized using descriptive (frequency, %) statistics by dose cohort. The primary endpoint of MTD cannot be established because the study was closed early, and, based on the observed safety profile with a single DTC occurring in dose cohort 4 (1/4 patients), future studies can consider dose level 3 as the starting dose.

### 13.5 Secondary Objectives, Endpoints, Analysis Plans

#### Secondary endpoints:

- a) To collect Polyphenon E/EGCG pharmacokinetic data in participants with cirrhosis.
- b) To determine the effects of Polyphenon E/EGCG treatment on the suppression of  $\gamma$ -hydroxy-1,N(2)-propanodeoxyguanosine ( $\gamma$ -OHPdG) levels in cirrhotic liver by LC-MS assay from baseline to post-treatment.
- c) To estimate the fraction of participants with liver cirrhosis that have high levels of  $\gamma$ -OHPdG.

We will test the  $\gamma$ -OHPdG levels at baseline and at the end of study in all subjects. Based on our preclinical models, we believe six months of intervention will decrease the  $\gamma$ -OHPdG levels. We will use two methods to measure the level of  $\gamma$ -OHPdG including IHC stain and Mass Spectrum analysis. The pathology slides prepared from the liver biopsy will be stained for antibody targeting  $\gamma$ -OHPdG. The level of  $\gamma$ -OHPdG will be scored from 0 to 6. IHC score of 0 to 2 is defined as  $\gamma$ -OHPdG low, and IHC score of 3 to 6 is defined as  $\gamma$ -OHPdG high. When  $\gamma$ -OHPdG is measured by mass spectrum, the absolute amount of  $\gamma$ -OHPdG will be measured. In this study, we hope to evaluate whether decrease in  $\gamma$ -OHPdG level will result in decrease in mutation frequency only in five subjects due to budget restriction. The data will help to test our hypothesis and support future studies. If there is no restriction in budget, we would like to carry out the study in all subjects.

For secondary outcome (b) LC-MS assay will be used to determine gamma-OHPdG changes from baseline to post-treatment. This will generate a continuous variable for values of gamma-OHPdG. Descriptive statistics (mean, range) will be used to summarize this continuous outcome by dose level. A nonparametric trend test will be used to examine whether there is a trend for greater reduction in gamma-OHPdG as the dose level increases.

For secondary outcome (c) we will use descriptive statistics to estimate the fraction of participants with liver cirrhosis that have high levels of  $\gamma$ -OHPdG. Participants will be screened for high levels of  $\gamma$ -OHPdG. Only participants with high levels of  $\gamma$ -OHPdG will be enrolled for intervention. The

fraction of participants with liver cirrhosis that have high levels of  $\gamma$ -OHPdG is calculated based on the number of subjects enrolled over the number of subjects screened based on the levels of  $\gamma$ -OHPdG in their first liver biopsy. This important information may help to estimate the portion of cirrhotic participants with high risk for HCC development, and can be used to design a future large chemoprevention study using Polyphenon E or other green tea extract in HCC prevention.

Due to the early stopping, secondary and exploratory endpoints will be summarized using descriptive statistics across dose cohorts. Changes in biomarkers across dose levels will be analyzed using a nonparametric trend test.

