### 1.2 Secondary Objectives

- 1.2.1 To collect Polyphenon E/EGCG pharmacokinetic data in participants with cirrhosis.
- 1.2.2 To determine the effects of Polyphenon E/EGCG treatment on the suppression of  $\gamma$ -hydroxy-1,N(2)-propanodeoxyguanosine ( $\gamma$ -OHPdG) levels in cirrhotic liver by LC-MS assay from baseline to post-treatment.
- 1.2.3 To estimate the fraction of participants with liver cirrhosis that have high levels of  $\gamma$ -OHPdG.

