## 8.2 Secondary Endpoints

8.2.1 To collect Polyphenon E/EGCG pharmacokinetic data in participants with cirrhosis.

In previous preclinical studies, the pharmacokinetics of the conjugated metabolites of EGC and EC were not affected by repeat green tea polyphenol daily treatment for 4 weeks. A limited sampling strategy was developed to predict EGCG pharmacokinetics after green tea administration (38). The median sampling times were 0.7, 1.4, and 7.0 hours (fasting conditions) and 1.4, 3.6, and 8.7 hours (fed conditions). The sampling schemes were accurate and precise in predicting EGCG

oral clearance and exposure (area under the curve [AUC]) under both fasting and fed conditions. In this current study, blood and urine samples will be collected in six subjects on day 1 of a 4 week cycle, prior to the first dose of Polyphenon E, and then at 1.5, 3.5, and 8.5 hours (+/- 5 minutes) after the first dose of Polyphenon E, taken while fed. Clearance of Polyphenon E will be compared among cirrhotic liver participants in this study and results from this population will be compared with non-cirrhotic historical control participants (38).

8.2.2 LC-MS assay will be used to determine gamma-OHPdG changes from baseline to post-treatment. This will generate a continuous variable for values of gamma-OHPdG. Descriptive statistics (mean, range) will be used to summarize this continuous outcome by dose level. A nonparametric trend test will be used to examine whether there is a trend for greater reduction in gamma-OHPdG as the dose level increases.

8.2.3 To estimate the fraction of participants with liver cirrhosis that have high levels of  $\gamma$ -OHPdG.

The fraction of participants with liver cirrhosis that have high levels of  $\gamma$ -OHPdG is calculated based on the number of subjects enrolled over the number of subjects screened based on the levels of  $\gamma$ -OHPdG in their first liver biopsy.

8.2.4 Exploratory Endpoint: To assess the effects of Polyphenon E on the grade of cirrhosis as measured by FibroScan and FIB-4 score.

Whether Polyphenon E treatment affects the level of cirrhosis will be evaluated by comparing the reading of FibroScan at baseline and 6 months of EGCG treatment in the subjects participating the intervention study.

8.2.5 Exploratory Endpoint: To develop an LC-MS and/or ELISA-based method for detecting  $\gamma$ -OHPdG.

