## **13. STATISTICAL CONSIDERATIONS**

### **13.1 Study Design/Description**

We propose a single-arm, multicenter MTD seeking, escalation study. To meet our primary goal, 2-48 participants with cirrhotic livers expressing high levels (score 3 and above) of  $\gamma$ -OHPdG ( $\gamma$ -OHPdG-high) in their baseline biopsy are required for the Polyphenon E intervention portion of the study.

In our unpublished data, 68 participants with cirrhosis, 38% (90% confidence interval, range 0.28, 0.49) of cirrhotic liver biopsies demonstrated high  $\gamma$ -OHPdG levels (IHC score  $\geq 3$ ). Therefore, a minimum of 4 and maximum of 171 participants with liver cirrhosis will be screened in our current study. A minimum of 2 and a maximum of 48 participants whose cirrhotic liver biopsies show a  $\gamma$ -OHPdG score  $\geq 3$  will be registered for treatment. If a maximum tolerated dose is established, a total of 24 participants will receive the maximum tolerated dose. The maximum tolerated dose is defined as the highest dose where no more than 1 of 6 participants experience an event meeting the Discontinue Therapy Criteria (DTC) during the first four weeks of treatment and the next higher dose is such that 2 or more participants had experienced an event meeting the DTC during the first four weeks of treatment.

Trial enrollment was stopped early, with 13 patients enrolled in Cohorts 1- 4 during dose escalation, of whom 10 participants had both pre- and post-treatment biopsies for biomarker assessment (Table 6). No participants were enrolled in the dose expansion cohort.

**Table 6:** Trial Enrollment

| Cohort         | Started Trt | Pre & Post Bx | DTC |
|-----------------------|--------------------|--------------------------|------------|
| Cohort 1 (400mg QD)   | 3                  | 3                        | 0          |
| Cohort 2 (400 mg BID) | 3                  | 3                        | 0          |
| Cohort 3 (600 mg BID) | 3                  | 2                        | 0          |
| Cohort 4 (800 mg BID) | 4                  | 2                        | 1          |

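### The LC-MS objective is a before-after question, but the only test assigned to it is a dose-trend test, which does not answer it

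*Combined protocol and SAP*

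**What the plan says.** Section 1.2 sets the objective as the effect of treatment on γ-OHPdG "levels in cirrhotic liver by LC-MS assay from baseline to post-treatment". Section 13.5 repeats it as secondary outcome (b).

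The analysis is given in the same words in 8.2.2 and 13.5:

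- The measurement: "LC-MS assay will be used to determine gamma-OHPdG changes from baseline to post-treatment".
- The summary: "Descriptive statistics (mean, range) will be used to summarize this continuous outcome by dose level".
- The test: "A nonparametric trend test will be used to examine whether there is a trend for greater reduction in gamma-OHPdG as the dose level increases".

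The early-stopping paragraph in 13.5 keeps this form. Secondary endpoints get descriptive statistics across cohorts, and "Changes in biomarkers across dose levels will be analyzed using a nonparametric trend test". The documents do not name the trend test, its alpha, its sidedness, or the scale on which change is computed.

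Section 13.1 reports 13 participants treated, "of whom 10 participants had both pre- and post-treatment biopsies for biomarker assessment". Table 6 divides these pairs as 3, 3, 2 and 2 over cohorts 1 to 4.

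A test against zero does appear in 13.4: a Wilcoxon test of post-minus-pre differences. It is described and sized in IHC score units, with a mean of 4 before treatment and an SD of 2.

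**The concern.** The objective concerns a change within participants. The test concerns whether that change differs between doses. The two can disagree in both directions:

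- An equal fall at every dose is a true effect on the objective and a true null for the trend test.
- A rise at the low doses that fades to no change at the top dose is a trend in the planned direction with no suppression anywhere.

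Section 9.1 calls IHC semi-quantitative and gives LC-MS the role of quantitative confirmation. As written, the confirming assay has no test or interval estimate aimed at the effect it is meant to confirm. The only p-value attached to it could be read as evidence for or against suppression, and it is neither.

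**Working it through.** **1. The plan's own power figures.** These are for the IHC Wilcoxon test in 13.4, with N = 24, SD = 2 and two-sided alpha 0.05. The effect sizes are 1.33/2 = 0.665 and 1.6/2 = 0.8. The Wilcoxon efficiency adjustment under normality gives 24 × 3/π = 22.9, truncated to 22. One-sample noncentral-t power with n = 22 is 0.84466 and 0.94694, which matches the plan to five decimals. The plan gives no power figure for the LC-MS trend test.

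**2. Trend test when all doses act equally.** The inputs are group sizes 3/3/2/2 (Table 6), with two-sided 0.05, no ties and all ten pairs usable taken as assumptions. There are 10!/(3!·3!·2!·2!) = 25,200 equally likely arrangements.

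| Test | Rejection probability |
|---|---|
| Jonckheere-Terpstra, two-sided | 3.75% |
| Cuzick-type linear rank test, two-sided | 3.98% |
| Jonckheere-Terpstra, one-sided 0.05 | 4.7% |

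A common shift leaves the ordering between groups unaffected, so these figures hold whatever the size of the common effect. They are test sizes.

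**3. Precision of the means.** The half-width of a 95% CI is t(0.975, n−1)/√n in SD units:

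- n = 2: 12.706/1.414 = 9.0
- n = 3: 4.303/1.732 = 2.5
- n = 10: 2.262/3.162 = 0.7

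**4. Simulated rejection rates, ten pairs.** Normal log(post/pre) was assumed. The documents give no LC-MS SD, so 0.3, 0.5 and 0.7 are assumptions. The 35% fall is the midpoint of the 30-40% expected in 13.4. The graded and rising patterns are illustrative. The trend test is Cuzick-type and both tests are two-sided.

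| True change by cohort | Trend test, SD 0.3 / 0.5 / 0.7 | Pooled signed-rank, SD 0.3 / 0.5 / 0.7 |
|---|---|---|
| Fall of 35% at every dose | 4% / 4% / 4% | 97% / 66% / 40% |
| Fall of 10 / 25 / 40 / 55% | 53% / 23% / 13% | 79% / 45% / 28% |
| Rise of 60 / 40 / 20 / 0% | 28% / 13% / 8% | (detects a rise) |

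As a second anchor, at the IHC effect sizes of 0.665 and 0.8 SD the pooled signed-rank test on ten pairs has about 45% and 60% power.

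**5. Fewest usable pairs.** The smallest exact two-sided signed-rank p-value is 2 × (1/2)ⁿ. It is 0.0625 for n = 5 and 0.031 for n = 6.

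**6. Regression to the mean.** Only participants with an IHC score of 3 or more are treated (4.1.7), and 38% of the earlier biopsies reached that level (13.1). Under normality, the mean of the top 38% lies φ(0.305)/0.38 = 1.00 SD above average. With no drug effect, the expected log fall is (1 − ρ) × r × 1.00 × s. Here ρ is the pre/post correlation, r the IHC/LC-MS correlation and s the baseline log-SD. The value ρ = 0.5 is the plan's assumption for IHC. The other values are assumed: ρ up to 0.8, r from 0.5 to 0.8, s from 0.5 to 0.8.

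- Smallest: 0.2 × 0.5 × 1.00 × 0.5 = 0.050, a fall of 5%.
- Largest: 0.5 × 0.8 × 1.00 × 0.8 = 0.32, a fall of 27%.

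In simulation over this range, the pooled signed-rank test rejects in 7% to 22% of null trials. The trend test stays at about 4%.

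**The case against.** Several points on the other side have force.

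- **The trend test does what it says.** It is offered as a dose-response test, and that is a reasonable question. A reader might take the 4% as poor power. It is the size of the test under a true null and would stay near alpha at any sample size. What is missing is a second analysis.
- **A uniform fall would not be hidden.** The planned table of means by dose would show it, and summaries across cohorts could include a pooled one. This stands, but nothing planned says how precisely the fall is estimated, and step 3 shows that the cohort means alone are nearly uninformative.
- **Other passages may cover it.** The Wilcoxon test in 13.4 is about γ-OHPdG in general terms, but its inputs are IHC scores, and 13.5 gives LC-MS a separate plan. A sentence in 13.5 promises 95% confidence intervals for estimates. It stands under the exploratory endpoint after demographics and safety, and is not tied to the LC-MS change.
- **The remedy has its own bias.** In a single arm selected for high baseline IHC, a pooled fall can arise without any drug effect (step 6). The caution in 13.6 covers background change over time and does not mention selection. This stands, and the fix must carry the warning.
- **Ten pairs is an upper limit.** Table 6 counts paired biopsies, not LC-MS results, and section 10.2 allows archival paraffin tissue in place of the fresh baseline biopsy.

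A reader might also infer that the plan analyses untransformed change. The documents do not say so; the scale is not stated.

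**Conclusion.** The concern holds and should be fixed. The analysis assigned to outcome (b) does not address objective 1.2.2. With equal effects at all doses, the planned test rejects about 4% of the time (3.7% to 4.7% over the trend tests and sidedness considered). When levels rise by 60/40/20/0% and nothing is suppressed, it rejects in about 28% of trials at a log-ratio SD of 0.3 and 13% at 0.5. Means by dose have CI half-widths of 2.5 to 9.0 SD, against 0.7 SD pooled over ten pairs.

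How much a pooled test would gain depends on an LC-MS SD that the documents do not give. Power is about 40% to 97% for a uniform 35% fall at assumed SDs of 0.7 to 0.3, or about 45% to 60% at the IHC effect sizes. All these figures assume ten usable pairs.

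It would go too far to say that the trial would miss or conceal a real suppression. The outcome is secondary, the trial stopped at 13 participants with mainly descriptive analyses, and the IHC measure has its own before-after test.

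**What to change.** In 13.5 and 8.2.2:

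1. Add a pooled paired analysis of LC-MS change over all evaluable pairs: the geometric mean post/pre ratio with a 95% CI, and an exact Wilcoxon signed-rank test on log(post/pre).
2. Keep the dose-trend test as the dose-response analysis, on the same log scale. Name the test, its alpha and its sidedness.
3. Plot every individual pair by dose level.
4. State the number of LC-MS-evaluable pairs, at most 10. With five or fewer, report the estimate and CI only, because the exact two-sided test cannot reach 0.05.
5. State that a trend alone is not evidence of suppression.

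In 13.6, add to the existing caution that a pooled fall in a single arm selected for high baseline IHC may partly reflect regression to the mean.

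The cost is SAP wording and one further analysis of data already planned, with no new samples or visits.

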### 3. SUMMARY OF STUDY PLAN

[figure not shown]
3.1 We propose a single arm, multicenter phase I study of subjects with cirrhotic livers expressing high levels (score 3 and above) of  $\gamma$ -OHPdG ( $\gamma$ -OHPdG-high) in their baseline biopsy (biopsy 1) who will receive Polyphenon E for 24 weeks. This study is a dose escalation design (see **Dose Escalation Schema** below). Participants in each cohort will be monitored for 4 weeks for Discontinue Therapy Criteria (DTC) before additional participants will be enrolled for the next dose cohort.

The Discontinue Therapy Criteria is defined as:

- a. Grade 3 or higher toxicity based on CTCAE criteria which is possibly, probably, or definitely related to the study agent OR
- b. Requires discontinuation of treatment based on the Hepatotoxicity Assessment Algorithm (Appendix D) OR
- c. Any hepatic decompensation such as
  1. New onset ascites or worsening of ascites (requiring increase in drug therapy or requiring surgical intervention such as paracentesis).
  2. Variceal bleeding documented by endoscopy
  3. Spontaneous bacterial peritonitis documented by positive culture
  4. Hepatic encephalopathy
  5. Hepatorenal syndrome (Type 1 or 2)
  6. Porto-pulmonary hypertension

7. Hepato-pulmonary hypertension
8. Any liver related event that leads to hospitalization or G4 event.

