will have one follow up visit to discuss the test result and surveillance plan. Liver biopsy is required for participants who have no archival liver biopsy tissue adequate for  $\gamma$ -OHPdG testing collected and stored within 12 months prior to consent. Participants with archival liver biopsy tissue adequate for  $\gamma$ -OHPdG testing, and collected and stored within 12 months prior to consent, may optionally have the liver biopsy at Screen 2. If the participant has archival liver biopsy tissue collected within the last 12 months prior to consent, the archival tissue can be tested (or sent for testing) for  $\gamma$ -OHPdG at either Screen 1 or Screen 2.

- k. Urine samples for compliance will be collected at Visit 2 and Visit 3. Urine sample for biomarker analysis will be collected at Screen 2 or Visit 1 if participant has archival biopsy.
- l. Two green and two purple top tubes are collected. At Visit 1, the Research Blood should be collected prior to agent administration.
- m. First six participants who consented for PK sample collection at Georgetown: Participants will be asked to fast after midnight except for drinking water prior to coming into the clinic. Blood and Urine samples for pharmacokinetic analysis will be obtained on Visit 1 (week 1 day 1) in clinic prior to Polyphenon E treatment, and at 1.5 hour, 3.5 hour, and 8.5 hours (+/- 5 minutes for blood PKs, and +/- 15 minutes for urine collection) for participants receiving Polyphenon E treatment after a light breakfast. Urine samples are self-collected as indicated in section 10.2.
- n. The Alcohol and Tobacco Assessments are found in Appendices E-H. The Baseline questionnaires (Appendices E & F) should be administered at Visit 1. The Follow-up Questionnaires (Appendices G & H) should be administered at Visit 3 or at the end of study treatment. Appendix I should be given to each participant upon completing the Alcohol and Tobacco Use Assessment the first time.
- o. Polyphenon E will be dispensed at Visit 1 (week 1 day 1) (3 month supply) and Visit 2 (week 13 +/- 3 days) (3 month supply). Participant diary will be collected when the drug is dispensed. Unused pills will be counted at Visit 2 (week 13 +/- 3 days) visit and Visit 3 (week 25 +/- 3 days).

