### **7.3 Evaluation During Study Intervention**

#### **Study Visit 1 (Week 1 Day 1)**

Participants will come to the clinic to receive study procedures and their first dose of study agent. Participants who volunteer for the PK tests at Georgetown will be asked to fast after midnight except for drinking water prior to coming into the clinic.

- Ultrasound, CT or MRI of the abdomen will be performed at Screen 1, Screen 2, or at Visit 1 prior to starting agent, if not performed within 3 months prior to consent
- FibroScan will be performed at Screen 1, Screen 2, or at Visit 1 prior to starting agent, if

- not performed within 3 months prior to consent
- If the participant is pre-menopausal and of child-bearing potential, and has not had a negative pregnancy test within 72 hours prior to starting study agent, another pregnancy test will be performed at this visit. If a test is performed, the result must be negative in order to start agent.
- Record Concomitant Medications
- Physical Exam & Vital Signs
- Adverse Events Assessments.
- Venipuncture for clinical labs
- Clinical Labs – including CBC with differential and platelets, comprehensive metabolic panel including BUN, creatinine, sodium, potassium, chloride, calcium, bicarbonate, glucose, liver function tests including AST, ALT alkaline phosphatase, total protein, albumin, direct bilirubin, indirect bilirubin, and total bilirubin, magnesium, GGT, and phosphorous, coagulation test (INR), AFP and AFP-L3.
- Administer the Alcohol and Tobacco Baseline Assessments (Appendices E & F)
- Provide participant with the participant diary (Appendix C), agent study drug instructions (Appendix B), and the resources handout (Appendix I).
- Research Blood (for  $\gamma$ -OHPdG level)
- Research Blood PKs (for the first six participants at Georgetown University who agree)
- Research Urine PKs (for the first six participants at Georgetown University who agree)
- Research Urine for  $\gamma$ -OHPdG level if participant had archival biopsy
- Dispensation of study drug

Study Visit 1 will be performed 0-14 days after registration.

### Between Visits 1 and 2

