### **Biopsies**

Of note, participants who are on chronic anticoagulation will be required to hold anticoagulation prior to the biopsies being performed. Participants on warfarin must hold treatment for 5 days, but will be on low-molecular weight heparin (LMWH), 1 mg/kg subcutaneously twice a day. LMWH

will continue until the evening prior to the biopsy. LMWH will be held in the morning of the procedure, but the patient will receive LMWH the evening of the day of biopsy. Participant may then resume warfarin the day of biopsy.

Preferred biopsy is core biopsy; 14 -18 gauge (G), 2.11-1.27 mm outer diameter (OD), 1.6-0.84 mm inner diameter (ID), 0.254-0.216 mm wall thickness, hypodermic needles can be used to perform the core biopsies based on the sites standard of care procedures. The use of a 16G needle is highly recommended as it is the most appropriate size to use for percutaneous liver biopsies (70,71). Twenty (20) unstained liver biopsy sections, cut 4-microns-thick must be submitted to the [name] laboratory at Georgetown University/Lombardi for assessment of  $\gamma$ -OHPdG levels in liver samples. Subjects with high levels of  $\gamma$ -OHPdG (IHC stain  $=/ > 3$ ) who meet all other eligibility criteria will then be receive Polyphenon E treatment. A random liver biopsy will be performed at 24 weeks (+/- 7 days) prior to end of treatment. The liver tissue will be evaluated by [name] laboratory at Georgetown University/Lombardi to assess for  $\gamma$ -OHPdG levels (Section 10.2). Liver biopsy samples will be stored in the lab of [name].  $\gamma$ -OHPdG testing of the liver biopsy will be carried out at least twice each month at [name] lab. The liver biopsy samples will be shipped Monday-Thursday, after communication with the receiving site.

Lastly, all liver biopsies taken during the course of the study, regardless of the indication (i.e., both protocol-defined and those performed for other clinical indications) must be assessed by the PIs and the pathologists at Georgetown University Hospital.

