## 9.2 Comparable Methods

In this study, we use IHC, a semi-quantitative method to measure the levels of  $\gamma$ -OHPdG in body tissues, and LC/tandem MS methodology, a quantitative method, to confirm these of  $\gamma$ -OHPdG levels. There are no other methods used to measure  $\gamma$ -OHPdG levels. Only one such comparison was reported (34) and we will compare the results from this study to those previously reported. We found that approximately 30% of cirrhotic participants expressed high levels of  $\gamma$ -OHPdG in their liver biopsies. We will be able to compare this previous observation with the data obtained in this current study.

The methods used for pharmacokinetic study and gene target sequencing are well-established procedures. No better methods exist for obtaining the data needed for this study.

The novelty of the study lies in our evaluation of the change of  $\gamma$ -OHPdG levels in participants treated with Polyphenon E using standard established methods.

$\beta$ -Catenin and p53 are the two most frequently mutated genes in HCC. Obtaining the mutation spectrum of  $\beta$ -Catenin and p53 is sufficient to evaluate the change of GC to TA and GC to AT mutations prior to and after Polyphenon E treatment. Measurement of the mutation spectrum of specific genes is less costly compared to whole genome sequencing.

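### The secondary endpoint for the fraction with high γ-OHPdG counts enrolled participants, not high scorers, so it measures enrolment yield and not prevalence

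*Combined protocol and SAP*

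**What the plan says.** Objective 1.2.3 is to estimate what share of participants with cirrhosis have high γ-OHPdG. Section 13.5 defines high as an IHC score of 3 to 6 on a 0 to 6 scale. Sections 8.2.3 and 13.5 then give the same formula: the fraction "is calculated based on the number of subjects enrolled over the number of subjects screened based on the levels of" γ-OHPdG in the first liver biopsy.

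Two places show what enrolled means here. In 13.5, shortly before the formula, only high scorers "will be enrolled for intervention". In 13.1, "Trial enrollment was stopped early, with 13 patients enrolled in Cohorts 1- 4 during dose escalation", and those 13 are the total of the column for starting treatment in Table 6 (3 + 3 + 3 + 4).

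Section 13.5 adds that the result may help estimate the portion of cirrhotic participants at high risk of HCC, and can be used to design a larger prevention study.

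**The concern.** Both uses named in 13.5 need a prevalence: of those whose liver was scored, how many scored 3 or more. Enrolled over tested answers a different question, namely how many treated participants the screening effort produced. The two agree only if every high scorer goes on to treatment.

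The plan does not guarantee that:

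- In 7.6 (Biopsies), high scorers "who meet all other eligibility criteria will then be receive Polyphenon E treatment", so a high score is necessary but not sufficient.
- The imaging that excludes HCC can follow the score. In 7.3, "Ultrasound, CT or MRI of the abdomen will be performed at Screen 1, Screen 2, or at Visit 1 prior to starting agent".
- Places are rationed. In 3.1, each cohort is watched for 4 weeks "before additional participants will be enrolled for the next dose cohort", while 4.4 and 13.3 aim to biopsy most candidates in the first few months.
- Accrual was stopped early (13.1), which could leave scored participants without a place.
- Participants may decline after learning their score.

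Anyone lost in these ways leaves the numerator and stays in the denominator. There is also a possible error the other way. Under 7.1 note j, participants with adequate archival tissue "may optionally have the liver biopsy at Screen 2". Someone low on archival tissue and high on the fresh sample could be enrolled, and so counted, although the first biopsy was low.

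**Working it through.** **Inputs.** Preliminary series: 26 of 68 high (2.3.4); 38%, 90% CI 0.28 to 0.49 (13.1). Planned numbers: up to 171 screened and 48 treated, at least 4 screened and 2 treated (13.1). Enrolled: 13 (13.1, Table 6). The number tested and the number of high scorers not enrolled are not in the documents, so any value used for them below is an assumption.

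**The plan's own figures.** 26/68 = 0.382. The exact (Clopper-Pearson) 90% interval is 0.284 to 0.489, which matches the stated interval. 48/0.28 = 171.4 and 2/0.49 = 4.1, which match 171 and 4. These divisions apply the proportion of high biopsies to the number screened, so screened is best read as biopsy-tested. The denominator therefore needs only clearer wording; the numerator is the problem.

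**Effect of the formula.** Let p be the true prevalence and g the share of high scorers not enrolled. The planned ratio has expectation p × (1 − g), a shortfall of p × g. With p = 0.38:

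| g (assumed) | Planned ratio | Shortfall (points) |
|---|---|---|
| 0 | 38.0% | 0 |
| 10% | 34.2% | 3.8 |
| 20% | 30.4% | 7.6 |
| 30% | 26.6% | 11.4 |

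The half-width of the stated 90% interval is (0.49 − 0.28)/2 = 0.105. Of these values, only g = 30% gives a shortfall larger than that.

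**In counts near this trial's size.** Take 13 enrolled and choose the number tested so that the true fraction is close to 38%:

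| High scorers not enrolled (assumed) | Tested (assumed) | Planned ratio | High over tested |
|---|---|---|---|
| 1 | 37 | 13/37 = 35.1% | 14/37 = 37.8% |
| 3 | 42 | 13/42 = 31.0% | 16/42 = 38.1% |
| 5 | 47 | 13/47 = 27.7% | 18/47 = 38.3% |

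The exact 95% interval for 16/42 is 0.236 to 0.544, about 15 points either side. The error in each row is smaller than that.

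**The reported figure cannot reveal the problem.** If 34 were tested, 13/34 = 38.2% would appear to confirm the preliminary value. Each high scorer not enrolled should add 1/34 = 2.9 points; three of them would make it 16/34 = 47.1%.

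**The case against.** The strongest reply is that this is loose terminology, not a chosen numerator. Section 2.5.3 places the baseline biopsy at enrolment, before any score exists. Section 3.1 speaks of high scorers being enrolled where the parallel sentence in 13.1 says registered for treatment. The screening numbers treat high scorers and treated participants as one set. The closing reference to the first biopsy could govern the whole ratio, which would make it high over tested.

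The routes of loss are also narrower than they first appear. Under 7.1 note a and 7.2, fresh biopsy waits for the Screen 1 laboratory results, so most laboratory failures never receive a fresh-biopsy score. Three weeks for scoring (4.4) plus a 4-week cohort hold (3.1) is 21 + 28 = 49 days, inside the 60-day laboratory window in 6.8. The upward route is doubtful, since 2.3.5 reports no crossing between low and high in 14 serial pairs. Finally, this is a descriptive endpoint in a trial that stopped at 13, and the size of any bias is assumed.

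Much of this stands as a limit on how often the two counts differ. It does not remove the defect. No section makes enrolment follow automatically from a high score, and none returns lost high scorers to the numerator. Late imaging, archival tissue scored as early as Screen 1, cohort holds and the early stop all remain. If high over tested was intended, the correction simply writes that down; an analyst following the present text would divide 13 by the number screened.

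**Conclusion.** The concern holds. As written, the endpoint is an enrolment yield and not the prevalence named in objective 1.2.3. This rests on reading enrolled as entered into treatment, which is how 13.5 and 13.1 use it. The expected direction is downward, with one unlikely route upward. The size is unknown and may be zero. The 3.8, 7.6 and 11.4 point shortfalls are illustrations that assume a true prevalence of 38% and losses of 10%, 20% and 30%. In a sample of about 40 such an error would usually be hidden by sampling variation, but a confidence interval does not correct it, and it would carry into the design of the later study. It should be corrected. It does not affect the primary endpoints.

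A side issue concerns the comparator. Section 9.2 says "approximately 30% of cirrhotic participants expressed high levels of" γ-OHPdG and that the trial's result will be compared with that observation, whereas 2.3.4 and 13.1 give 38% (26/68). Section 9.2 does not say which series it means. This adds no weight to the numerator problem.

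**What to change.** In 8.2.3 and 13.5:

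- Define the numerator as all participants whose first biopsy, baseline or archival, has an IHC score of 3 or more, whether or not they were enrolled or treated.
- Define the denominator as all participants with an evaluable first-biopsy IHC score.
- State which biopsy counts as first when both archival and Screen 2 tissue exist.
- Report the fraction with the 95% confidence interval already called for in 13.5, preferably exact, and list high scorers not treated with the reasons.
- If enrolment yield is of interest, report it separately under that name.

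In 9.2, reconcile the earlier prevalence with the 26/68 in 2.3.4 and 13.1, or identify the series it comes from.

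The cost is a sentence or two in two sections and one figure in 9.2. No new data are required, since the IHC score exists for everyone tested.
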